13.10 Analysis Approach

13.10.1 Software

All calculations will be performed using SAS statistical software, version 9.1 or later, and StatXact, version 10 or later.

13.10.2 Display Formats

All efficacy and safety data will be displayed in tables and listings. Separate analyses will be performed for Stage 1, Stage 2, and for combined stages (primary efficacy endpoint). Post-Text TLFs will be provided in collated electronic MS Word .rtf files (i.e. table columns and rows appear in MS Word Table format).

13.10.3 Conventions

Means, mean changes, standard deviations, and ranges will be presented separately for Stage 1 and then for each Stage 2 treatment group over time. These endpoints will be evaluated within the three study treatment groups for the change from Stage 1 and Stage 2 baselines using a paired t-test and between study treatment groups using an unpaired t-test at each time; these p-values will be presented as descriptive statistics.

For continuous variables, the mean, standard deviation, minimum, median and maximum will be presented, together with the total number of observations and the number of missing and non-missing values. Unless otherwise specified minimum and maximum values will be reported to the same number of decimal places as the recorded measurements, mean and median are reported to one more decimal place and standard deviation one additional decimal place more than the mean.

For ordinal and categorical variables, absolute and relative frequencies will be reported. Relative frequencies will be based on all observations and reported as percentages to one decimal place. Unless otherwise specified percentages will be based on the number of subjects with data and will not be calculated for missing categories.

Adverse events, medical histories and concomitant medications will be reported on a subject and an event basis. The percentages will be calculated using the number of subjects in the population Analysis Set as the denominator.

All hypotheses will be tested at 5% (final analysis) level of significance using a two-sided test unless otherwise specified.

P-values will be rounded to four decimal places. If a p-value is less than 0.0001 it will be reported as “<0.0001.” If a p-value is greater than 0.9999 it will be reported as “>0.9999”.

13.10.4 General Methodology

Time to event analyses will be performed using a Kaplan-Meier lifetable, two-sided Wilcoxon-Gehan test, and proportional hazard models (PHREG) including the following covariates: study treatment, C-SSRS 24 hours post infusion (1,2, or 3), age (<25, 25-39, >40), and gender. The proportional hazard model results for the Intention-to-treat (ITT) population will be considered to be the primary analysis for the primary efficacy endpoint while the MMRM results for the ITT population will be considered to be the primary analysis for the secondary efficacy endpoints.

All of the instruments used to measure ASIB or depression constitute serial continuous and ordinal outcomes which will be analyzed using Mixed-Effect Model Repeated Measure (MMRM) to account for missing data and early discontinuations. The models will include treatment group, study visit, the interaction between study visit and treatment group, the baseline of the variable being analyzed, C-SSRS 24 hours post infusion (1, 2, or 3), age (<25, 25-39, >40), and gender as fixed effects. The reason for missing data will be evaluated as a condition of MMRM analysis.

An autoregressive (AR1) variance covariance structure will be assumed for this analysis. To account for mis-specification of the covariance structure, the Liang and Zeger’s “sandwich” estimator (via the EMPIRICAL option in SAS PROC MIXED) will be used. Restricted maximum likelihood (REML) will be used to estimate all parameters and will be the basis for all hypothesis testing (SAS default). For the primary model including the interaction term, the hypothesis test to perform on the fixed effects will be Type III (SAS® option htype = 3). SAS® PROC MIXED will be used.

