4.3 Rationale for Clinical Development Plan

To meet the unmet need for the treatment of ASIB in adults with BD, NeuroRx, Inc. is developing NRX-101, a fixed-dose combination oral capsule composed of d-cycloserine (DCS) and lurasidone, intended as a component of a sequential therapy, which takes advantage of a unique synergistic confluence of three FDA-approved drugs with long histories of safety.

The combination of the drugs for the proposed sequential therapy (DCS, lurasidone, ketamine) has been tested in an acute toxicity study under a protocol reviewed in advance by FDA and found to have no evidence of neurotoxicity, even at otherwise toxic doses (i.e. 2000 mg/kg) of lurasidone. Each of the proposed drugs has a long history of safe use in humans and their AE profiles are well characterized. The safety of the three drugs, given in combination has been tested in a human phase 2 study that was deemed IND-exempt by FDA.

DCS is a broad spectrum antibiotic approved for the treatment of tuberculosis (TB). DCS has been used in millions of individuals without report of significant safety concerns.

Lurasidone is an atypical antipsychotic with approval for the treatment of depressive episodes associated with bipolar depression. Of the other drugs in its class, lurasidone requires the lowest treatment dose and demonstrates the fewest side effects.

Ketamine is a nonbarbiturate, rapid-acting general anesthetic for intravenous (IV) or intramuscular injection, approved for surgical anesthesia. Ketamine has a wide margin of safety. Its use for more than 12,000 types of operative and diagnostic procedures was studied in over 10,000 subjects participating in 105 separate clinical studies.

Ketamine has been shown in multiple randomized clinical trials to induce nearly immediate remission from acute suicidality and depression, however the clinical effect has been demonstrated to diminish at 3 days post-dose. Whereas Ketamine is a direct NMDA channel blocker which binds to the PCP binding site, DCS in high doses has an NMDA antagonist effect by binding to the glycine site. This effect is apparently unrelated to its properties as an anti-infective. By combining the potential of DCS to extend the anti-depressant effects of ketamine with the antipsychotic properties of lurasidone ([Stone et al., 2009](#)), NRX-101 has potential to stabilize individuals with bipolar depression during acute crisis and address a serious medical need.

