8.2.5 Outcome and Safety Measures

8.2.5.1 Outcome Measures

8.2.5.1.1 Primary Efficacy Endpoint

The primary outcome measure will be time to relapse, defined as (1) a return to a score of ≥ 4 on the C-SSRS, (2) a score of ≥ 20 on the MADRS subset of the BISS following a response to

ketamine at 24 hours, or (3) the treating physician's determination that a change in treatment plan, such as re-hospitalization, ECT, or addition of new antidepressant drugs is required.

All site-defined relapses will be adjudicated by a Relapse Adjudication Committee (RAC) which will review documentation provided by the site for each incidence and determine whether the relapse meets the protocol definition of relapse. The RAC will meet monthly. The RAC is authorized to determine that relapse occurred even if the site does not make this determination.

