13.8 Sample Size Calculations

13.8.1 Allocation

To encourage study participation, a 2:1:1 randomization will be used where at most half as many subjects will be assigned to the lurasidone and placebo arms as compared to the K/N study arm. The goal will be to have 62 subjects randomized to K/N and 31 subjects randomized to each of K/L and K/P for a total of 124 randomized subjects. The randomization takes place among Ketamine responders once confirmed by Medical Monitor.

13.8.2 Stage 1

The study goal is to achieve a total of 124 Ketamine responders for the Stage 2 evaluation. A total of 192 subjects are projected to be enrolled but this number may be reached sooner if the cumulative effect of the Ketamine response rate exceeding 70%, if the Stage 1 loss rate being less than 8% (15 subjects), or if the Stage 2 loss rate being less than 8% (9 subjects). Thus, there would be 177 subjects who complete Stage 1 before considering Ketamine response. The literature and prior experience suggests that 70% of those treated with ketamine will have an adequate reduction in depression and suicidality which equates to 124 Ketamine responders (177×0.7) who would be available for randomization. More subjects will need to be enrolled if the Ketamine response rate was lower than 70% or the randomization refusal rate was higher than 8%, considered to be part of Stage 2 losses.

13.8.3 Stage 2

Stage 2 will investigate the study hypotheses. The primary efficacy hypothesis is that K/N will delay the time to relapse relative to K/L and K/P. The goal will be to have 62 subjects randomized to K/N and 31 subjects randomized to K/L and K/P. These numbers are based on the Ketamine Responders. See **Error! Reference source not found.** for the total number of K/N and K/L subjects required to test the primary efficacy hypothesis. The sample size requirements are shown just for K/N and K/L. .

The study is powered based on the number of subjects randomized to K/N vs. K/L. In order to achieve 90% study power with two-sided 0.05 Type I error, a total of 56 K/N subjects, 28 K/L subjects, and 28 K/P subjects must be evaluated for time to relapse over the full 6 weeks. This is based on the assumption of a 30% relapse rate in the K/N treatment group and a 70% relapse rate in the K/L and K/P treatment groups. A larger gap in the relapse rate is expected based on the literature, so this is believed to be a conservative assumption. These calculations assume a loss of 8% during Stage 2.

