13.9 Overall Type 1 Error Control

The overall Type I error is two-sided 5%. No interim analyses are planned.

A hierarchical testing plan is in place to control Type I error to extend labeling claims in the following pre-defined testing order where statistical significance (two-sided $p < 0.05$) is required at each step:

1. Primary: K/N will delay time to relapse relative to K/L and K/P
2. Secondary: K/N will separate from K/L and K/P by 72 hours, with sustained difference between groups thereafter

3. Secondary: All-cause discontinuation (including discontinuation for continued suicidal ideation) will be lower in K/N than K/L and K/P.
4. Secondary: K/N will separate from K/L and K/P starting at Day 7, with sustained difference thereafter
5. Secondary: Improvements within the K/N group observed at Week 2 will remain stable to end of study.

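### The primary PHREG model for time to relapse names no tie method, although relapses found at scheduled ratings will share dates; naming Efron is a small, free improvement

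*Combined protocol and SAP*

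**What the plan says.** Section 13.10.4 specifies "proportional hazard models (PHREG) including the following covariates: study treatment, C-SSRS 24 hours post infusion", age and gender, and adds: "The proportional hazard model results for the Intention-to-treat (ITT) population will be considered to be the primary analysis for the primary efficacy endpoint". Section 13.10.5 repeats the model and counts time from the day of the infusion. Section 11 also names it. None of the three gives a tie method. Section 13.10.1 says only "All calculations will be performed using SAS statistical software, version 9.1 or later". The repeated-measures model for the secondary endpoints, by contrast, is specified down to covariance structure, variance estimator and hypothesis-test type.

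Section 8.2.5.1.1 lists three relapse components: a C-SSRS threshold, "a score of ≥ 20 on the MADRS subset of the BISS", and the treating physician's decision that the treatment plan must change. After randomisation, Table 3 schedules the C-SSRS on Days 6 (by phone), 7, 10, 14, 21, 28, 35 and 42, and the BISS on the same days from Day 7. Neither scale is scheduled on Days 2 to 5.

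**The concern.** A relapse first detected by a scheduled rating will naturally take that visit's date, so several subjects will share an event time. Two features of the protocol could concentrate relapses at the first visits. On ketamine, section 4.3 says "however the clinical effect has been demonstrated to diminish at 3 days post-dose", which falls in the gap before Day 6. Also, response needs only a 25% fall in the MADRS subset, while relapse is a score of 20 or more. A subject with a baseline of 27 or above (20/0.75 = 26.7) can therefore count as a responder, still score 20 or more, and meet the threshold at the first BISS on Day 7.

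The Cox partial likelihood needs a convention for ties, and the common approximations differ when ties are heavy. The primary hazard ratio and p-value would then depend on an undeclared option, and the testing hierarchy in section 13.9 starts from that p-value.

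**Working it through.** **Inputs.** Section 13.8.3: "a total of 56 K/N subjects, 28 K/L subjects, and 28 K/P subjects must be evaluated for time to relapse over the full 6 weeks"; planned rates are a "30% relapse rate in the K/N treatment group and a 70% relapse rate in the K/L and K/P treatment groups". Alpha is two-sided 0.05 (section 13.9). Visit days are from Table 3.

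**The plan's own figures.** Table 12 defines h = ln(p1)/ln(p2), with p1 and p2 the relapse-free proportions on K/L and K/N.
- 30% vs 70%: ln(0.30)/ln(0.70) = 3.376, as stated.
- 30% vs 52%: ln(0.30)/ln(0.52) = 1.841, as stated.
- Expected pairwise relapses at the planned rates: 28 × 0.70 + 56 × 0.30 = 19.6 + 16.8 = 36.4. Adding K/P gives 36.4 + 19.6 = 56.0 over three arms.
- Schoenfeld power, planned rates: √(36.4 × 1/3 × 2/3) × ln(3.376) − 1.96 = 2.844 × 1.217 − 1.96 = 1.50, or 93.3%.
- Table 12's 90% power column (h = 1.841, 48 relapses) does not reproduce: √(48 × 2/9) × ln(1.841) − 1.96 = 0.03, or about 51%.

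**Why the tie method matters.** At a date with d tied relapses, let R be the sum of exp(βx) over everyone at risk and D the same sum over those who relapse. Breslow uses the denominator R^d. Efron uses the product over l = 0, …, d−1 of (R − (l/d)D). Breslow keeps all tied subjects in every factor, so the denominator is too large and the estimate moves toward no effect.

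**Simulation.** 28 K/L vs 56 K/N, 10,000 trials per scenario, treatment as the only covariate, no losses, two-sided Wald test. Visit-detected relapses are moved to the next of Days 6, 7, 10, 14, 21, 28, 35 and 42. Three dating patterns were run: every relapse on an exact visit day; the same with visits varying by 1 day either way; and half the relapses dated to the actual day. The hazard is constant or front-loaded (Weibull shape 0.5). The hazard ratio is K/L over K/N (median estimate).

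| True HR | Hazard | Dating | HR Breslow | HR Efron | Power Breslow | Power Efron | Loss (points) |
|---|---|---|---|---|---|---|---|
| 3.376 | constant | exact visits | 3.190 | 3.376 | 94.6% | 95.5% | 0.9 |
| 3.376 | constant | ±1 day | 3.313 | 3.385 | 95.5% | 95.8% | 0.3 |
| 3.376 | constant | half off-visit | 3.318 | 3.388 | 95.1% | 95.4% | 0.3 |
| 3.376 | front-loaded | exact visits | 3.087 | 3.374 | 94.1% | 95.5% | 1.4 |
| 3.376 | front-loaded | ±1 day | 3.263 | 3.375 | 95.1% | 95.6% | 0.5 |
| 3.376 | front-loaded | half off-visit | 3.280 | 3.400 | 95.0% | 95.6% | 0.6 |
| 1.841 | constant | exact visits | 1.778 | 1.845 | 49.0% | 53.2% | 4.2 |
| 1.841 | constant | ±1 day | 1.819 | 1.845 | 52.0% | 53.8% | 1.8 |
| 1.841 | constant | half off-visit | 1.817 | 1.843 | 51.7% | 53.6% | 1.9 |
| 1.841 | front-loaded | exact visits | 1.749 | 1.857 | 45.7% | 54.2% | 8.5 |
| 1.841 | front-loaded | ±1 day | 1.799 | 1.840 | 50.3% | 53.0% | 2.7 |
| 1.841 | front-loaded | half off-visit | 1.798 | 1.841 | 50.2% | 53.4% | 3.2 |

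With no treatment difference (30% relapse-free in both arms) and constant hazard, Breslow vs Efron rejects in 3.1% vs 5.0% of trials (exact visits), 4.2% vs 4.7% (±1 day) and 4.5% vs 5.2% (half off-visit). Front-loaded with exact visits, it is 2.3% vs 4.7%. The Monte Carlo standard error is about 0.2 points near 95% and 0.5 near 50%.

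Untied continuous times give 3.385 and 95.6% in the first row, so Efron recovers nearly everything that Breslow loses.

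**The case against.** The strongest reply is that the exact-visit rows are a worst case that the protocol does not describe. Relapse includes a physician's decision that can fall on any day, and section 13.10.5 has relapse judged in real time. Discharged subjects are contacted twice daily in the first week (8.1), daily symptom contact is planned (8.2.5.2.3), and visits have windows. This stands. A reader might infer from Table 3 that nobody is observed on Days 2 to 5 and that all relapses fall on eight dates; the documents do not support that. Once dates spread, most of the effect disappears.

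It is also fair that nothing in the documents says Breslow will be used. The unstated method is a fact of the text; the Breslow result is conditional on a software assumption.

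A reader might also cite the 4- to 9-point losses at 1.841 as the cost to this trial. That effect comes from the Table 12 column that does not reproduce, whereas the text of 13.8.3 plans on 30% vs 70%. At 1.841, power is near 50% under either method, for reasons unrelated to ties.

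Finally, a tie option could be regarded as programming detail. That does not fully answer the point: the plan gives this level of detail for the secondary model, and the omission concerns the primary one.

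**Conclusion.** This is a minor specification gap with a free remedy. Under assumed Breslow ties, the primary hazard ratio at the planned effect would be understated by about 2% when dates spread (3.31 vs 3.39, constant hazard), 6% with all relapses on exact visit days (3.19 vs 3.38), and 9% if the hazard is also front-loaded (3.09 vs 3.37). The power cost is 0.3 to 1.4 points, and power stays at 94% or more in every planned-effect scenario. Losses of about 2 to 9 points arise only at smaller effects such as 1.84.

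The error is conservative: type I error falls below 5%. It would be wrong to conclude that a positive result is in doubt.

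These sizes rest on the assumed default, the assumed hazard shapes and share of visit-dated relapses, no losses, no covariates beyond treatment, and a pairwise K/N vs K/L fit. A single three-arm model was not simulated.

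**What to change.** In 13.10.4 and 13.10.5, state that the primary PHREG model uses TIES=EFRON (or EXACT). In the same place, state the date assigned to a relapse first seen at a scheduled visit, including one that the Relapse Adjudication Committee declares when the site did not. A discrete-time complementary log-log model on the visit intervals would be a reasonable sensitivity analysis, but it is optional.

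The cost is one procedure option and one or two sentences, settled before unblinding. Sample size, visits, data collection and clinical conduct do not change.

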The 2013 Heresco-Levy study provided initial evidence that DCS might be useful as an NMDAR- targeted antidepressant, but the time of onset for DCS alone was suboptimal for treating acutely depressed individuals. Therefore, an open-label study was performed in which subjects with bipolar depression received an infusion of ketamine on Day 1, followed by oral administration of DCS, titrated to a dose of 1000mg/day combined with lurasidone 66mg/day as individual commercially-supplied medications. Seven of 8 subjects completed the study and no adverse effects were noted. Over a period of 8 weeks, a > 75% reduction in suicidal ideation and a 50% reduction in depression was noted, using the Hamilton Depression Scale (HAM-D). (Figure 2; [Kantrowitz, 2015](#)). Note that suicidal ideation was eliminated entirely at 4 hours post-infusion of ketamine (Figure 3; [Kantrowitz, 2014](#)).

Figure 2 Depression Score after Ketamine followed by DCS + 5-HTZASource: [Kantrowitz, 2015](#)**Figure 3** Suicidal Ideation after Ketamine followed by DCS + 5-HTZASource: [Kantrowitz, 2014](#)

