6.2 Methods

[figure not shown]
In Stage 1 eligible subjects will initially receive an infusion of open-label ketamine 0.5mg/Kg. Those who do not respond to ketamine infusion as measured by a $\geq 25\%$ improvement in the MADRS subset on the BISS and a reduction in C-SSRS suicidal ideation to ≤ 3 at 24 hours post infusion will be withdrawn from the study and treated according to standard of care for subjects with suicidal ideation or behaviors.

Subjects who respond successfully to ketamine infusion, as defined above ($\geq 25\%$ improvement in the MADRS subset of the BISS and C-SSRS ≤ 3) at 24 hours post infusion will proceed to Stage 2 and be randomized to either experimental drug NRX-101 (DCS + lurasidone), lurasidone alone, or placebo. Efficacy data will be collected for the subjects responding to ketamine through 6 weeks or until earlier rescue.

Subjects may be terminated from the study and rescued with alternative therapy at any time if, in the opinion of the investigator, subjects have a significant safety risk for clinical deterioration or suicide.

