The study protocol does not dictate the site of care (inpatient vs. outpatient). That is determined by the treating physician in consultation with the patient and family, based upon assessment of the patient's acuity, the patient's home environment, and other factors that psychiatrists expert in the management of this patient population use in determining the appropriate site of care. It is anticipated that subjects enrolled at C-SSRS level 4 are likely to be managed in the outpatient setting, whereas those enrolled at C-SSRS level 5 will be maintained under continuous professional observation until they have stabilized at a C-SSRS level 3 or lower. Just as site of care is determined by the treating physician, the decision to discharge those subjects who begin in the inpatient setting is entirely up to the study physician, based upon the same protocols and criteria already in place to determine discharge for patients with suicidal bipolar depression. The study sponsor and the study protocol will not influence this decision in any way. The sponsor does require, however, that subjects with C-SSRS level 5 ideation or behavior be under continual professional observation from the time of enrollment and ketamine infusion to the point at which the patient is deemed to have stabilized and is randomly assigned to one of the study arms.

All eligible subjects will receive ketamine infusion according to the procedures in this protocol. All infusions will be conducted in a clinic-like or hospital setting with a licensed anesthetist, standard monitoring equipment, and full emergency backup available. Subjects who experience sufficient improvement and are stable after the ketamine infusion may be hospitalized or discharged at the discretion of the treating physician. Discharge will only be allowed if there is an established support structure and agreement to follow the safety plan whereby sites will contact subjects twice daily for the next week either in person or through a video connection provided by sponsor and then at least weekly through the end of the study to collect study data to support efficacy and safety. The election to follow subjects who respond to initial ketamine on an inpatient or outpatient basis will be made by the treating study physician with the consent of the subject.

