8.1.6 Randomization

Subjects will be assessed in person 24 hours post-infusion for response to ketamine. Those who do not respond will be provided standard of care for ongoing suicidal ideation. Following the documented observance of a therapeutic response to intravenous ketamine as defined by a 25% or greater reduction in the on the MADRS subset of the BISS score and a score of ≤ 3 on the C-SSRS at 24 hours post infusion, subjects will be randomized 2:1:1 to either a fixed dose combination of experimental drug NRX-101 (DCS + lurasidone), or to an identical capsule containing placebo + lurasidone, or to an identical capsule containing placebo. Randomization blocks will be allocated at the site level to ensure that treatment and control groups are balanced per site. An Interactive Web Response System will be used.

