8.2.3 Randomization phase

Following the documented observance of a therapeutic response to IV ketamine as defined by a 25% or greater reduction in the baseline MADRS and a C-SSRS ≤ 3 at 24 hours post infusion, subjects will be randomized 2:1:1 to either a fixed dose combination of experimental drug NRX-101 (DCS + lurasidone) or to an identical capsule containing placebo + lurasidone or to an identical capsule containing placebo. Institution balancing will be used to ensure that treatment and control groups are balanced with stratification according to C-SSRS 24 hours post-infusion (1, 2). Subjects who respond to ketamine will be followed for 6 weeks or until they require additional treatment.

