9.3 Randomization/Method of Assigning Subjects to Treatment

Following the documented observance of a therapeutic response to intravenous ketamine as defined by a 25% or greater reduction in the MADRS score and a score of ≤ 3 on the C-SSRS, at 24 hours post infusion, patients will be randomized 2:1:1 to either a fixed dose combination of DCS + lurasidone (NRX-101), to an identical capsule containing placebo+lurasidone, or to an identical capsule containing placebo. Site blocking will be used to ensure that treatment and control groups are balanced per site.

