13.2 Randomization

Following the documented observance of a therapeutic response to intravenous ketamine as defined by a 25% or greater reduction in the MADRS score and a score of < 3 on the C-SSRS, at 24 hours post infusion, patients will be randomized 2:1:1 to either a fixed dose combination of DCS + lurasidone (NRX-101), to an identical capsule containing placebo+lurasidone, or to an identical capsule containing placebo. Site blocking will be used to ensure that treatment and control groups are balanced per site.

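### The 24-hour C-SSRS factor is coded (1, 2, or 3) in Section 13.10.4 but (1, 2) in the stratification rule and elsewhere, so a level-3 responder has no stratum and the MMRM has two specifications

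*Combined protocol and SAP*

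**What the plan says.** The 24-hour post-infusion C-SSRS score appears as a factor in four places in the design: randomisation, the primary Cox model, the MMRM and the Poisson safety model.

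- Section 13.10.4 lists the Cox covariates as "study treatment, C-SSRS 24 hours post infusion (1,2, or 3), age (<25, 25-39, >40), and gender". It repeats the three C-SSRS levels for the MMRM, which it names as the primary analysis of the secondary efficacy endpoints.
- Section 8.2.3 calls for institution balancing with "stratification according to C-SSRS 24 hours post-infusion (1, 2"), and no third level.
- Sections 11 and 13.10.6 describe the MMRM with levels (1, 2). Sections 8.2.5.2.3, 13.7.2 and 13.10.8 do the same for the Poisson model.

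On who can be randomised, Section 6.2 requires "a reduction in C-SSRS suicidal ideation to ≤ 3 at 24 hours post infusion". Sections 8.1.6, 8.2.3 and 9.3 also use 3 or below, and Section 8.1 speaks of observation "until they have stabilized at a C-SSRS level 3 or lower". Section 13.2 alone prints "a score of < 3 on the C-SSRS, at 24 hours post infusion".

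On the method of randomisation, Section 8.1.6 says "Randomization blocks will be allocated at the site level to ensure that treatment and control groups are balanced per site" and Section 9.3 says "Site blocking will be used to ensure that treatment and control groups are balanced per site". Section 13.2 has the same sentence as 9.3. None of these three mentions a C-SSRS stratum.

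**The concern.** The randomisation system needs a stratum for every responder on the day of randomisation, and the models should adjust for the same factor in the same form. Under the rule of 3 or below, a subject at level 3 is a valid responder, yet the stratification list has no place for that subject. Someone would have to improvise: merge level 3 with level 2, add a stratum, or leave the subject unstratified.

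Two programmers could also fit different MMRMs and both claim to follow the plan. Sections 6.4 and 13 promise that all analyses are prespecified before enrolment. If the coding is settled after data are seen, that promise is weakened for the analyses that feed the hierarchical tests of the secondary endpoints.

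**Working it through.** **1. Codings side by side**

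| Use | Section | C-SSRS levels | Top age band as printed |
|---|---|---|---|
| Stratification | 8.2.3 | 1, 2 | none |
| Primary Cox model | 13.10.4 | 1, 2, 3 | >40 |
| MMRM | 13.10.4 | 1, 2, 3 | >40 |
| MMRM | 11 and 13.10.6 | 1, 2 | >40 |
| Poisson safety model | 8.2.5.2.3 and 13.7.2 | 1, 2 | ≥40 |
| Poisson safety model | 13.10.8 | 1, 2 | >40 |

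Counted by analysis, Cox has three levels, the MMRM has both lists, and Poisson and stratification have two. A lost symbol cannot explain this, because a whole level is present in one list and absent from the other.

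**2. Levels against eligibility.** Section 8.2.6.1 describes a 1-to-5 ideation scale. Under the rule of 3 or below, the eligible printed scores are 1, 2 and 3. The list in 13.10.4 covers all three; the (1, 2) list leaves out 3. Under the rule printed in 13.2 the eligible scores would be 1 and 2, and (1, 2) would cover them. The factor therefore cannot be settled until the responder passages agree.

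**3. No ideation.** No list names a category for a responder with no ideation, and the documents print no score of 0. Section 4.5 reports, from an open-label study of 8 subjects, that "suicidal ideation was eliminated entirely at 4 hours post-infusion of ketamine". That is a different time point and a very small study, but it makes the state foreseeable.

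**4. Planned size.** 28 / 0.92 = 30.4, rounded up to 31; 31 × 4 = 124, which matches Section 13.8. For K/N against K/L, expected relapses are 56 × 0.30 + 28 × 0.70 = 36.4. The hazard ratio is ln(0.30)/ln(0.70) = 3.376. Schoenfeld power at 2:1 is Φ(√(36.4 × 2/9) × ln 3.376 − 1.96) = Φ(3.46 − 1.96) = 93.3%, above the planned 90%.

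**5. Parameters in the pairwise Cox model.** Treatment 1, C-SSRS (three levels) 2, age 2, gender 1: 6 in all, or 36.4/6 = 6.1 events per parameter. A fourth C-SSRS category, or a Day-1 MADRS term, makes 7 (36.4/7 = 5.2). Both together make 8 (36.4/8 = 4.55). Two C-SSRS groups plus MADRS make 6.

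**6. Effect of adding Day-1 MADRS.** Simulation of 56 against 28 subjects, relapse-free 70% against 30%, full 13.10.4 covariate list with C-SSRS, age and gender assumed not prognostic, 10,000 runs (Monte Carlo error about 0.2 point):

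| Assumed log-HR per SD of MADRS | Power without | Power with | Change (points) |
|---|---|---|---|
| 0 | 95.1% | 94.9% | −0.2 |
| 0.3 | 95.1% | 95.7% | +0.6 |
| 0.5 | 95.5% | 97.3% | +1.8 |

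A second simulation gave −0.2, +0.4 and +1.6. The documents give no prognostic strength, so the range is an assumption. A link with relapse is plausible: a baseline score of 27 that falls by 25% is 20.25, which is already at the relapse threshold of 20 in Section 8.2.5.1.1.

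**The case against.** The best case on the other side is that the primary analysis is intact. Section 13.10.4 governs the Cox model, and its three levels cover every printed score eligible under the rule of 3 or below. That stands, and it limits the point to stratification, the MMRM and the safety model.

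Second, some of the discrepancies may be artefacts of text extraction. The same randomisation sentence has ≤3 in 9.3 and <3 in 13.2, and the same alternative hypothesis has ≥ in 5.1 and > in 13.4.1. The printed >40, which leaves age 40 without a band, fits that pattern. This also stands: the age band is a typographic note only, and the <3 may be no more than that.

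Third, three randomisation sections name site blocking without C-SSRS. A reader might infer that C-SSRS stratification has been dropped. The documents do not support this, because none of the three says site only and 8.2.3 adds C-SSRS. Confirmation is all that is needed.

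Fourth, a reader might infer that level-3 subjects would fall out of the analysis, or that crossing site with C-SSRS makes the blocks too thin. No section states a rule that drops such subjects. Block size, site sizes and the distribution of levels are not given, and thin cells would be a complaint about over-stratification, not about this inconsistency.

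Finally, the plan is not wrong to omit Day-1 MADRS. The BISS looks back 7 days (Section 8.2.6.1), so a 24-hour score partly reflects the period before the infusion.

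**Conclusion.** The inconsistency is real and can be read directly from the text. One factor has two level lists. Section 8.2.3 admits level 3 and gives it no stratum. The MMRM is specified in two ways. The missing stratum depends on the responder rule of 3 or below, which four sections print as a threshold and Section 8.1 states in words; it would not arise under 13.2 as printed.

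The consequence is ambiguity in randomisation and in the secondary and safety models. The documents do not support a claim of lost subjects, bias or material power loss, or of a defect in the primary Cox list. It should be corrected because the correction is cheap before enrolment and cannot be made cleanly afterwards.

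The Day-1 MADRS term is a separate improvement of modest size: about −0.2 to +2 power points at the planned relapse rates, for an assumed log-HR per SD between 0 and 0.5.

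**What to change.** 1. Reconcile the responder threshold across Sections 6.2, 8.1.6, 8.2.3, 9.3 and 13.2.
2. State in every randomisation section whether C-SSRS stratification applies together with site blocking.
3. Before enrolment, fix one C-SSRS coding that places every eligible responder, including one with no ideation, in a category. The 13.10.4 list extended to no ideation would serve, and so would a prespecified grouping of it. Use it identically in the randomisation system and in the Cox, MMRM and Poisson models.
4. Print the top age band as ≥40 throughout, as in 8.2.5.2.3 and 13.7.2.
5. Optionally, add the Day-1 MADRS subset score as a continuous covariate in the primary Cox model. Table 3 schedules the BISS on Day 1, and Section 8.1.6 uses that score before randomisation, so no new data are needed.

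Items 1 to 4 cost only wording in the protocol, SAP and randomisation specification. A fourth C-SSRS category adds one parameter to the Cox model; a two-group coding saves one but adjusts more coarsely. Item 5 adds one parameter, makes the hazard ratio conditional on that score, and costs about 0.2 power point if the score is not prognostic.
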